1.1 RAD001 (everolimus)

RAD001 (everolimus) is a novel oral derivative of rapamycin.

RAD001 has been in clinical development since 1996 as an immunosuppressant in solid organ transplantation and has obtained marketing authorization (Certican®) for prophylaxis of rejection in renal and cardiac transplantation in a number of countries, including the majority of the European Union. RAD001 has been in development for patients with various malignancies since 2002. RAD001 2.5mg, 5mg and 10mg tablets were approved under the trade name Afinitor® for patients with advanced renal cell carcinoma (RCC) after failure of treatment with Sutent® (sunitinib) or Nexavar® (sorafenib) in the US, EU and several other countries and is undergoing registration in other regions worldwide. Afinitor® was also recently approved for the treatment of patients with subependymal giant cell astrocytoma (SEGA) associated with tuberous sclerosis (TS) who require therapeutic intervention but are not candidates for curative surgical resection.

RAD001 is being investigated as an anticancer agent based on its potential to act:

- Directly on the tumor cells by inhibiting tumor cell growth and proliferation
- Indirectly by inhibiting angiogenesis leading to reduced tumor vascularity (via potent inhibition of tumor cell HIF-1 activity, VEGF production and VEGF-induced proliferation of endothelial cells). The role of angiogenesis in the maintenance of solid tumor growth is well established, and the mTOR pathway has been implicated in the regulation of tumor production of proangiogenic factors as well as modulation of VEGFR signaling in endothelial cells.

1.1.1 mTOR pathway and mechanism of action

At cellular and molecular levels, RAD001 acts as a signal transduction inhibitor. RAD001 selectively inhibits mTOR (mammalian target of rapamycin), a key and highly conservative serine-threonine kinase, which is present in all cells and is a central regulator of protein synthesis and ultimately cell growth, cell proliferation, angiogenesis and cell survival. mTOR is the only currently known target of RAD001 (Reviewed in Boulay and Lane 2007).

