3.2.3 Interruption or discontinuation of treatment

For patients who are unable to tolerate the protocol-specified dosing schedule, dose adjustments are permitted in order to keep the patient on study drug. If administration of RAD001 must be interrupted because of unacceptable toxicity, drug dosing will be interrupted or modified according to rules described in Table 3-1. Toxicity will be assessed using the NIH-NCI Common Terminology Criteria for Adverse Events, version 3.0 (CTCAEv3.0, (<http://ctep.cancer.gov/forms/CTCAEv3.pdf>)).

Table 3.0 RAD001 dose level modification guidelines

Dose level	Dose and schedule
0 (starting dose)	10 mg daily
-1	5 mg daily
-2	5 mg every other day

Table 3-1 Criteria for dose-modification in case of suspected RAD001 toxicity and re-initiation of RAD001 treatment

Toxicity	Actions
Non-hematological toxicity	
Grade 2 (except pneumonitis – refer to Table 3-2)	If the toxicity is tolerable to the patient, maintain the same dose. If the toxicity is intolerable to patient, interrupt RAD001 until recovery to grade ≤ 1 . Then reintroduce RAD001 at same dose. If event returns to grade 2, then interrupt RAD001 until recovery to grade ≤ 1 . Then reintroduce RAD001 at the lower dose level.
Grade 3 (except hyperlipidemia*) (except pneumonitis – refer to Table 3-2)	Interrupt RAD001 until recovery to grade ≤ 1 . Then reintroduce RAD001 at the lower dose level. For pneumonitis consider the use of a short course of corticosteroids.
Grade 4	Discontinue RAD001.
Hematological toxicity	
Grade 2 Thrombocytopenia (platelets $<75, \geq 50 \times 10^9/L$)	Interrupt RAD001 until recovery to grade ≤ 1 ($>75 \times 10^9/L$). Then reintroduce RAD001 at initial dose. If thrombocytopenia again returns to grade 2, interrupt RAD001 until recovery to grade ≤ 1 . Then reintroduce RAD001 at the lower dose level.
Grade 3 Thrombocytopenia (platelets $<50, \geq 25 \times 10^9/L$)	Interrupt RAD001 until recovery to grade ≤ 1 (platelets $\geq 75 \times 10^9/L$). Then resume RAD001 at one dose level lower. If grade 3 thrombocytopenia recurs, discontinue RAD001.
Grade 4 Thrombocytopenia (platelets $< 25 \times 10^9/L$)	Discontinue RAD001.

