Agents containing hydrogen peroxide, iodine, and thyme derivatives may tend to worsen mouth ulcers. It is preferable to avoid these agents. Antifungal agents must be avoided unless a fungal infection is diagnosed. In particular, systemic imidazole antifungal agents (ketoconazole, fluconazole, itraconazole, etc.) should be avoided in all patients due to their strong inhibition of RAD001 metabolism, therefore leading to higher RAD001 exposures. Therefore, topical antifungal agents are preferred if an infection is diagnosed. Similarly, antiviral agents such as acyclovir should be avoided unless a viral infection is diagnosed.

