3.3 Treatments

3.3.1 RAD001 Administration

The study drug RAD001 will be self-administered (by the patients themselves). The investigator will instruct the patient to take the study drug exactly as specified in the protocol. RAD001 will be administered orally as once daily dose of **10 mg (two 5 mg tablets)** continuously from study day 1 until progression of disease or unacceptable toxicity. Patients will be instructed to take RAD001 in the morning, at the same time each day.

RAD001 may be taken with or without food.

If vomiting occurs, no attempt should be made to replace the vomited dose.

All dosages prescribed and dispensed to the patient and all dose changes during the study must be recorded.

Medication labels will comply with US legal requirements and be printed in English. They will supply no information about the patient. The storage conditions for study drug will be described on the medication label.

RAD001 will be provided by Novartis. RAD001 is formulated as tablets for oral administration of 5 mg and 10mg strength. Tablets are blister-packed under aluminum foil in units of 10 tablets (16 units per box), which should be opened only at the time of administration as drug is both hygroscopic and light-sensitive.

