3.3.3 Concomitant therapy

All concomitant medications administered within 14 days of enrollment through treatment termination should be reported to the investigator and recorded in the Case Report Form (CRF). In particular, corticosteroid dosing will be recorded as use of corticosteroids may affect the appearance of T2 changes on MRI imaging. In addition, the definition of response is based on corticosteroid use (see section 3.42).

Patients will be instructed not to take any additional medications (including over-the-counter products) during the course of the study without prior consultation with the investigator. At each visit, the investigator will ask the patient about any new medications he/she is or has taken after the start of the study drug.

All Concomitant medications/Significant non-drug therapies taken \leq 30 days prior to start and after start of study drug, including physical therapy and blood transfusions, should be recorded.

The following restrictions apply during the entire duration of the study:

- No other investigational therapy should be given to patients.
- No anticancer agents other than the study medication should be given to patients. If such agents are required for a patient then the patient must first be withdrawn from the study.
- Oral contraceptives in preclinical and clinical data have shown everolimus to have CYP3A4 inhibitory activity rather than induction activity, induction of metabolism of contraceptive hormones by everolimus is unlikely. Consequently, administration of everolimus should not reduce the efficacy of oral contraceptives.

Inhibitors of CYP3A4 and/or PgP

- Co-administration with strong inhibitors of CYP3A4 (e.g., ketoconazole, itraconazole, ritonavir) or P-glycoprotein (PgP) should be avoided

- Seville orange, star fruit, grapefruit and their juices affect P450 and PgP activity. These juices are potent CYP3A4-inhibitors. Concomitant use should be avoided
- Co-administration with moderate CYP3A4 inhibitors (e.g., erythromycin, fluconazole) or PgP inhibitors should be used with caution. If patient requires co-administration of moderate CYP3A4 inhibitors or PgP inhibitors, reduce the dose of RAD001 to 2.5 mg daily. Additional dose reductions to every other day may be required to manage toxicities. If the inhibitor is discontinued the RAD001 dose should be returned to the dose used prior to initiation of the moderate CYP3A4/PgP inhibitor after a washout period of 2 to 3 days.

Inducers of CYP3A4 and/or PgP

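### The 2.5 mg daily interaction dose in Section 3.3.3 cannot be dispensed from the study supply described in Section 3.3.1, and fluconazole has two conflicting classes and handling rules

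*Combined protocol and SAP*

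**What the plan says.** **Interaction dose.** For a patient who needs a moderate CYP3A4 inhibitor or a PgP inhibitor, Section 3.3.3 says to "reduce the dose of RAD001 to 2.5 mg daily". It then adds: "Additional dose reductions to every other day may be required to manage toxicities". After the inhibitor stops, the previous dose is resumed following a short washout.

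**Supply.** Section 3.3.1 says the drug supplier provides the study drug and that "RAD001 is formulated as tablets for oral administration of 5 mg and 10mg strength". It builds the starting dose from two 5 mg tablets. On the blister units it says "which should be opened only at the time of administration as drug is both hygroscopic and light-sensitive".

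**Other strengths.** A 2.5 mg tablet appears only in the background on the marketed product. Section 1.1 says "RAD001 2.5mg, 5mg and 10mg tablets were approved", and Section 1.1.3.3 repeats the point.

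**Toxicity levels.** Table 3.0 in Section 3.2.3 lists 10 mg daily, 5 mg daily and "5 mg every other day". Several rows of Table 3-1 restart treatment at a lower level.

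**Fluconazole.** Section 3.2.5.1 says "systemic imidazole antifungal agents (ketoconazole, fluconazole, itraconazole, etc.) should be avoided in all patients due to their strong inhibition of RAD001 metabolism", and prefers topical agents if a fungal infection is diagnosed. Section 3.3.3 names fluconazole as an example of a moderate inhibitor, to be used with caution and with the dose change above. Table 3-3 also lists it as moderate, and gives a class only, with no dose instruction.

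**The concern.** The interaction rule is a safety instruction for patients whose exposure to the drug is expected to rise. If the instructed dose cannot be dispensed from the supply the protocol describes, whoever treats the patient has to work out what to do without guidance from the plan. Section 3.4.8 states that drug levels are not monitored, so no measured concentration would show whether the adjustment had worked.

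Fluconazole raises a related problem. The need for an antifungal is foreseeable, because Section 3.2.5 itself warns of fungal infection under this drug. Two investigators reading different sections could handle the same prescription differently and each believe they were following the protocol.

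**Working it through.** No sample size, power or error rate enters this point, so there is no figure of the plan's to reproduce. The check is simple dose arithmetic and a side-by-side reading.

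**Step 1: which daily doses whole tablets can give.** Inputs are the 5 mg and 10 mg strengths in Section 3.3.1. With *a* tablets of 5 mg and *b* of 10 mg, the daily dose is 5*a* + 10*b*, which gives 5, 10, 15, 20 mg and so on. The smallest non-zero dose is 5 mg, so 2.5 mg is not reachable. By contrast, the inducer rule in Section 3.3.3 moves from 10 mg to 20 mg in 5 mg steps, and those doses are reachable (10 + 5 = 15; 10 + 10 = 20). The supply problem is therefore specific to the inhibitor rule.

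**Step 2: whether another source is provided.** The 2.5 mg tablet is mentioned only as an approved commercial strength. No section adds it to the study supply, and no section describes splitting tablets. The handling note in Section 3.3.1 concerns when to open the blister; it neither permits nor forbids splitting.

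**Step 3: mean daily dose against Table 3.0.**

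| Regimen | Source | Mean mg/day |
|---|---|---|
| 10 mg daily | Table 3.0, level 0 | 10 |
| 5 mg daily | Table 3.0, level -1 | 5 |
| 5 mg alternate days | Table 3.0, level -2 | 5 / 2 = 2.5 |
| 2.5 mg daily | Section 3.3.3 | 2.5 |
| 2.5 mg alternate days | Section 3.3.3, read in sequence | 2.5 / 2 = 1.25 |

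The interaction dose has the same mean as level -2 but a different unit dose and schedule. For a patient already at level -2, the instruction to reduce leaves the mean unchanged (2.5 against 2.5). The further step, if it means 2.5 mg on alternate days, falls below every level in the table and again needs a 2.5 mg unit.

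**Step 4: Table 3-1 for a patient on the interaction dose.** Suppose such a patient has a toxicity for which Table 3-1 restarts treatment at a lower level. Table 3.0 has no entry at 2.5 mg daily from which to count down. Section 3.3.3 mentions alternate-day dosing to manage toxicity, but neither section says whether that is the lower level Table 3-1 intends.

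**Step 5: fluconazole side by side.**

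| Place | Class | Instruction |
|---|---|---|
| Section 3.2.5.1 | strong inhibition, grouped with ketoconazole and itraconazole | avoid in all patients |
| Section 3.3.3 | moderate | caution; dose change if needed |
| Table 3-3 | moderate (ketoconazole and itraconazole listed as strong) | none |

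The class matters because Section 3.3.3 ties its rule to it: strong inhibitors are to be avoided and no adjusted dose is given, while moderate ones get the dose change. Changing the class changes the instruction.

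**The case against.** **Table 3.0 governs toxicity, not interactions.** This stands. Section 3.2.3 is about patients who cannot tolerate treatment, and the inducer doses of up to 20 mg also lie outside the table. A reader might infer that the absence of 2.5 mg from Table 3.0 is itself a contradiction, or that dose records will not fit the plan. The documents do not support either inference. Section 3.3.1 requires all prescribed doses and dose changes to be recorded, without limiting them to table levels. What remains is the narrower gap in Step 4.

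**The 2.5 mg tablet exists.** This stands in part. The strength is approved and the drug comes from its manufacturer, so it would be too strong to say the dose can never be given. The supportable statement is that the described supply does not yield it and nothing explains how it would be dispensed. One sentence might settle this.

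**Fluconazole can be read as avoid first, then adjust if unavoidable.** The protocol writes its inducer rule in that form, and Section 3.2.5.1 is advice rather than an absolute ban. That reading softens the conflict but does not remove it. The strong and moderate labels still disagree, and Section 3.3.3 opens its moderate rule with caution, not avoidance. Although Section 3.2.5.1 deals with mouth ulcers, its wording covers all patients.

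**The consequences are speculative.** This stands as far as size is concerned. Section 3.3.3 asks patients to consult the investigator before taking any new medicine, which offers some protection. It does not tell the investigator how to supply the dose.

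**Conclusion.** The point holds in two parts. First, the inhibitor dose in Section 3.3.3 cannot be carried out from the supply described in Section 3.3.1, and the next step down under Table 3-1 is undefined for a patient taking it. Second, fluconazole carries conflicting classes and conflicting instructions.

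The first part assumes whole tablets and no separate supply of the commercial 2.5 mg strength, since the documents provide for neither splitting nor that supply. The 1.25 mg/day figure also assumes that alternate-day dosing is a further step from 2.5 mg.

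The rule applies to any patient needing a moderate CYP3A4 inhibitor or a PgP inhibitor; the documents do not say how many that would be. A reader might go further and infer that unmanaged exposure would distort the discontinuation-based stopping rule in Section 6.1.1 or the 6-month result. The documents contain nothing from which to estimate such an effect, and none is claimed on sample size, power or the primary analysis. This is an inconsistency in a safety instruction that should be corrected, and correcting it is inexpensive.

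**What to change.** 1. Reconcile Sections 3.3.1 and 3.3.3 so that the instructed interaction dose, including any alternate-day step, can be dispensed from the stated study supply.
2. State how the lower-level instructions in Table 3-1 apply to a patient on the interaction dose. Table 3.0 itself need not list that dose.
3. Reconcile Sections 3.2.5.1 and 3.3.3 and Table 3-3 so that fluconazole has one class and one handling rule.

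Which dose and which rule apply is for the sponsor and investigators to decide; nothing here favours one. The cost is a few sentences of protocol wording or a supply clarification, handled through the amendment process in Section 4. No statistical section needs to be recalculated.

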1.1.3 Clinical experience

1.1.3.1 RAD001 Pharmacokinetics

Everolimus is rapidly absorbed with a median t_{max} of 1-2 hours. The steady-state $AUC_{0-\infty}$ is dose-proportional over the dose range between 5 to 70 mg in the weekly regimen and 5 and 10 mg in the daily regimen. Steady-state was achieved within two weeks with the daily dosing regimen. C_{max} is dose-proportional between 5 and 10 mg for both the weekly and daily regimens. At doses of 20 mg/week and higher, the increase in C_{max} is less than dose proportional. In healthy subjects, high fat meals reduced systemic exposure to everolimus 10 mg (as measured by AUC) by 22% and the peak plasma concentration C_{max} by 54%. Light fat

meals reduced AUC by 32% and C_{max} by 42%. Food, however, had no apparent effect on the post absorption phase concentration-time profile.

The blood-to-plasma ratio of everolimus, which is concentration-dependent over the range of 5 to 5,000 ng/mL, is 17% to 73%. The amount of everolimus confined to the plasma is approximately 20% at blood concentrations observed in cancer patients given everolimus 10 mg/day. Plasma protein binding is approximately 74% both in healthy subjects and in patients with moderate hepatic impairment.

Everolimus is a substrate of CYP3A4 and a substrate and moderate inhibitor of PgP. Following oral administration, everolimus is the main circulating component in human blood and is considered to contribute the majority of the overall pharmacologic activity. No specific excretion studies have been undertaken in cancer patients; however, data available from the transplantation setting found the drug to be mainly eliminated through the feces. There was a significant correlation between $AUC_{0-\infty}$ and pre-dose trough concentration at steady-state on the daily regimen. The mean elimination half-life of everolimus is approximately 30 hours.

Table 3-3 (Section 3.3.3) lists examples of clinically relevant CYP3A inhibitors and inducers.

Please refer to Section 3.3.3 for more information on the concomitant use of CYP3A4 inhibitors/inducers and other medications.

More information on RAD001 pharmacokinetics is provided in the [Investigator's Brochure].

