Avoid the use of strong CYP3A4 inducers. If patient requires co-administration of strong CYP3A4 inducers (i.e., phenytoin, carbamazepine, rifampin, rifabutin, Phenobarbital, St. John's wort), an increase in the dose of everolimus from 10mg daily to 20mg daily, using 5mg increments. Enzyme induction usually occurs within 7-10 days, therefore everolimus dose should be increased by one increment 7 days after the start of the inducer therapy. If no safety concerns are seen within the next 7 days, the dose can be increased again one additional increment up to a maximum of twice the daily dose used prior to initiation of the strong CYP3A4 inducer. This dose adjustment of RAD001 is intended to achieve similar AUC to the range observed without inducers. However, there are no clinical data with this dose adjustment in patients receiving strong CYP3A4 inducers. If the strong inducer is discontinued the RAD001 dose should be returned to the dose used prior to initiation of the strong CYP3A4/PgP inducer.

- No chronic treatment with systemic steroids (at a dose equivalent of greater than 20 mg prednisone per day) or other immunosuppressive agents. Topical or inhaled corticosteroids are allowed.
- The use of live vaccines and close contact with those who have received live vaccines should be avoided during treatment with everolimus. Examples of live vaccines include intranasal influenza, measles, mumps, rubella, oral polio, BCG, yellow fever, varicella and TY21a typhoid vaccines.

Oral anticoagulants such as warfarin are CYP2C9 substrates and, as such, no interaction with RAD001 is expected. However, drug-drug interaction studies between macrolide antibiotics and warfarin have produced mixed outcomes and the disparity in these findings has led to the conclusion that multiple factors may alter the clearance of warfarin. The coadministration of RAD001 and oral anticoagulants is possible but should be subject to verification of coagulation (INR) once steady state is reached (after one week's treatment).

Examples are provided in Table 3-3 (CYP3A4 inhibitors/inducers) and Table 3-6 (Drug interactions mediated by P-glycoprotein). A comprehensive list of cytochrome P450 isoenzymes and CYP3A4 inhibitors, inducers, and substrates can be found at

<http://medicine.iupui.edu/flockhart>. This website is continually revised and should be checked frequently for updates.

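### The fixed 2.5 mg daily dose for patients who need a moderate CYP3A4/PgP inhibitor gives no upfront cut in average dose at level -2, and matches neither the dose table nor the tablets listed

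*Combined protocol and SAP*

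**What the plan says.** Table 3.0 in Section 3.2.3 defines three dose levels: 10 mg daily (level 0, the starting dose), 5 mg daily (level -1) and "5 mg every other day" (level -2). Tables 3-1 and 3-2 move patients down these levels for toxicity.

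Section 3.3.3 covers interactions. It says that moderate CYP3A4 inhibitors "or PgP inhibitors should be used with caution". If a patient needs one, the instruction is to "reduce the dose of RAD001 to 2.5 mg daily". It then adds: "Additional dose reductions to every other day may be required to manage toxicities". When the inhibitor stops, the dose is to be "returned to the dose used prior to initiation of the moderate CYP3A4/PgP inhibitor" after a washout of 2 to 3 days. The instruction does not mention the patient's current level.

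On supply, Section 3.3.1 says: "RAD001 is formulated as tablets for oral administration of 5 mg and 10mg strength".

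**The concern.** The instruction is worded as a reduction, but it names a single absolute dose. Whether it reduces anything depends on where the patient starts. At level -2 the average daily dose is already 2.5 mg, so following the text exactly leaves it unchanged while an inhibitor of the drug's metabolism or transport is added. Under Tables 3-1 and 3-2 a patient normally reaches level -2 by stepping down for toxicity, so the rule gives the least upfront adjustment to patients who have already tolerated the drug poorly.

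The situation is plausible. Table 3-3 lists erythromycin, diltiazem and verapamil among the moderate inhibitors. The PgP table adds azithromycin, carvedilol, captopril and nifedipine. Section 3.2.5 names infections among the common reactions to the drug. Drug levels are not monitored (Section 3.4.8). After the first two months, laboratory tests are monthly and clinic visits are every two to three months (Section 3.4.1.2). A rise in exposure would therefore show mainly through its effects.

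There is also a practical conflict for every patient who needs an inhibitor: the dose named in Section 3.3.3 is not a Table 3.0 level, and whole tablets of the strengths listed in Section 3.3.1 cannot make it up.

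**Working it through.** The plan states no figure on this point to reproduce, so the check works from its doses.

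**Inputs from the documents**
- Level 0: 10 mg daily. Level -1: 5 mg daily. Level -2: 5 mg every other day (Table 3.0).
- Dose with a moderate inhibitor: 2.5 mg daily (Section 3.3.3).
- Half-life: "The mean elimination half-life of everolimus is approximately 30 hours" (Section 1.1.3.1).

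**Input not in the documents**
- F, the fold increase in exposure caused by the inhibitor. Assumed range: 1.5 to 5.

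**Step 1: average daily dose.** Dose per administration divided by the interval in days: 10/1 = 10; 5/1 = 5; 5/2 = 2.5 mg per day.

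**Step 2: cut on moving to 2.5 mg daily.** Cut = 1 - 2.5 / prior average.
- Level 0: 1 - 2.5/10 = 75%
- Level -1: 1 - 2.5/5 = 50%
- Level -2: 1 - 2.5/2.5 = 0%

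**Step 3: average exposure relative to the patient's own level before the inhibitor.** Ratio = F x 2.5 / prior average. This assumes dose-proportional exposure. Section 1.1.3.1 reports that for 5 and 10 mg daily, so its use at 2.5 mg is an extrapolation.

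| Level | F = 1.5 | F = 2 | F = 3 | F = 4 | F = 5 |
|---|---|---|---|---|---|
| 0 | 0.38 | 0.50 | 0.75 | 1.00 | 1.25 |
| -1 | 0.75 | 1.0 | 1.5 | 2.0 | 2.5 |
| -2 | 1.5 | 2.0 | 3.0 | 4.0 | 5.0 |

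At any F, the ratio at level -2 is four times the ratio at level 0 (10/2.5 = 4). The unequal treatment of the levels therefore does not depend on the assumed F; only its absolute size does.

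**Step 4: the further every-other-day step.** If it means 2.5 mg per dose, the average is 2.5/2 = 1.25 mg per day. The cuts become 87.5%, 75% and 50% at levels 0, -1 and -2. At level -2 the exposure ratio is then F x 0.5, or 0.75 to 2.5 over the assumed range.

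**Step 5: does splitting the dose matter at level -2?** A one-compartment steady-state model with k = ln 2 / 30 per hour gives peak = D / (1 - exp(-k x interval)) and trough = peak - D, in relative units.
- 5 mg every 48 h: peak 7.46, trough 2.46
- 2.5 mg every 24 h: peak 5.87, trough 3.37

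Before any inhibitor effect, the peak falls by about 21% (5.87/7.46 = 0.79) and the trough rises by about 37% (3.37/2.46 = 1.37). Average exposure does not change.

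**Step 6: tablets.** The smallest strength in Section 3.3.1 is 5 mg, so 2.5 mg daily would need half a tablet or a strength not listed there.

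**The case against.** The strongest reply is that the rule does not stand alone. Section 3.3.3 asks for caution, applies only when the inhibitor is required, tells patients to consult the investigator before taking any new medication, and allows a further step to every other day to manage toxicity. Section 3.2.5.1 says systemic imidazole antifungals, fluconazole among them, should be avoided, and Section 3.3.3 says the same of grapefruit. All of this stands. A reader might infer that a level -2 patient has no protection, or that the only safeguard comes after toxicity; the text supports neither. What the reply does not supply is a defined reduction at the start of co-administration for that patient. The cautions name no dose, and the every-other-day step is discretionary and reactive.

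A second reply is that the subgroup is small. It needs a patient at level -2 who also requires such an inhibitor, in a trial of 60, and several routes in Table 3-1 end treatment before level -2 is reached. The documents give no count, so this also stands; it limits the weight of the point but does not remove it.

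A third is that a 2.5 mg tablet exists: Section 1.1 mentions it as an approved strength. However, Section 3.3.1, which describes what the trial is provided with, does not list it.

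A reader might also set this rule against the inducer rule, which runs "up to a maximum of twice the daily dose used prior to initiation of the strong CYP3A4 inducer", and conclude that only the inhibitor rule ignores the current level. That contrast is weak: the inducer text also gives an absolute step from 10 mg to 20 mg daily, and only its ceiling is relative.

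**Conclusion.** The point holds in a limited form. As written, the inhibitor rule cuts the average daily dose by 75%, 50% and 0% at levels 0, -1 and -2. These figures rest only on the protocol's own doses. At level -2 the instruction to reduce has no effect on average dose, although the single dose halves. The documents do not say how the rule is meant to apply at levels -1 or -2. Separately, 2.5 mg daily appears neither in Table 3.0 nor as a dose that the listed whole tablets can deliver.

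The exposure ranges (0.38 to 1.25, 0.75 to 2.5 and 1.5 to 5 times at levels 0, -1 and -2) depend on the assumed 1.5- to 5-fold interaction and on dose-proportionality below 5 mg. A reader might infer a 4-fold interaction from the 75% cut at full dose. The documents do not support that: Section 3.3.3 states an aim of matching exposure for inducers only, and no section gives a size for the inhibitor effect.

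A reader might also infer that the discontinuation stopping rule in Section 6.1.1 would be affected. Nothing in the documents shows this. The number of patients concerned is unknown and probably small. This is a gap in a safety instruction that should be closed; it does not bear on the sample size or the primary analysis.

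**What to change.** Reconcile Table 3.0 (Section 3.2.3), the tablet strengths in Section 3.3.1 and the inhibitor instruction in Section 3.3.3. The revised instruction should state what applies to a patient at each of levels 0, -1 and -2 when a moderate CYP3A4 or PgP inhibitor is required, including whether co-administration is allowed at level -2. It should make clear what the every-other-day step means at each level, and it should agree with the dose table and the tablets supplied. The clinical team decides the content; this review proposes no dose.

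The cost is a wording amendment with the usual sponsor and IRB review. No extra visits, tests or patients are needed. If the team keeps a dose that the listed tablets cannot deliver, the supply description would have to change too.

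### When a strong CYP3A4 inducer or a moderate inhibitor stops, RAD001 goes back to its earlier dose, with no exception for a toxicity reduction made in between

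*Combined protocol and SAP*

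**What the plan says.** **Inducers (section 3.3.3).** Strong CYP3A4 inducers are to be avoided. If one is required, RAD001 may go from 10 mg to 20 mg daily in 5 mg steps. The first step comes 7 days after the inducer starts; the second may follow after another 7 days without safety concerns, "up to a maximum of twice the daily dose used prior to initiation of the strong CYP3A4 inducer". The aim is stated: "This dose adjustment of RAD001 is intended to achieve similar AUC to the range observed without inducers". The section adds that no clinical data support this adjustment. When the inducer stops, "the RAD001 dose should be returned to the dose used prior to initiation of the strong CYP3A4/PgP inducer".

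**Moderate inhibitors (section 3.3.3).** RAD001 is cut to 2.5 mg daily. Then: "Additional dose reductions to every other day may be required to manage toxicities". The next sentence, which also sets a washout of 2 to 3 days, reads: "If the inhibitor is discontinued the RAD001 dose should be returned to the dose used prior to initiation of the moderate CYP3A4/PgP inhibitor".

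**Toxicity (section 3.2.3).** Table 3.0 has three levels: 10 mg daily, 5 mg daily, and 5 mg every other day. After a grade 3 non-hematological event, Table 3-1 interrupts treatment until recovery and continues: "Then reintroduce RAD001 at the lower dose level". After a first grade 2 thrombocytopenia the instruction is "Then reintroduce RAD001 at initial dose".

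Nothing in sections 3.2.3, 3.2.4, 3.2.5.4 or 3.3.3 says which rule prevails when both apply, or bars a dose increase after a toxicity reduction.

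**The concern.** The return rules look back only to the dose before the interacting drug was started. A reduction made before that point is safe, because it is already the earlier dose. A reduction made during co-administration is not mentioned and is lost if the sentence is followed as written.

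The stake is patient safety. Someone who has just had a grade 3 event could be taken back to the dose or exposure at which it occurred. Drug levels are not measured (section 3.4.8), so this would show only through new symptoms, routine laboratory results or the monthly case review. A recurrence can also end treatment: under Table 3-1 a second grade 3 thrombocytopenia or febrile neutropenia means permanent discontinuation, which section 6.1.1 counts in the toxicity stopping rule.

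A second gap sits beside the first. Section 3.3.3 allows 15 and 20 mg, but Table 3.0 stops at 10 mg, so the next level down from those doses is not defined.

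**Working it through.** The plan gives no figure on this point to reproduce. The check follows the rules in order and adds simple dose arithmetic.

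**Inputs**
- Levels of 10 mg daily, 5 mg daily and 5 mg every other day (Table 3.0).
- On-inducer doses from a 10 mg start: 10, 15 and 20 mg; cap 2 × 10 = 20 mg (section 3.3.3).
- Fold induction f. Doubling the dose for a similar AUC implies f = 20/10 = 2. The range 1.5 to 3 is an assumption; the plan gives none.
- AUC proportional to dose. Section 1.1.3.1 supports this for daily dosing only at 5 and 10 mg; extending it to 20 mg is an assumption.

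**Step 1: reduced dose below the earlier dose, inducer.** A grade 3 event occurs at 10 mg in the first 7 days, before any increase. Table 3-1 with Table 3.0 gives 5 mg. When the inducer stops, section 3.3.3 gives 10 mg. Tablet dose: 10/5 = 2 times the reduced dose. No value of f enters.

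**Step 2: the same, moderate inhibitor.** 10 mg becomes 2.5 mg daily for the interaction, then 2.5 mg every other day for toxicity (1.25 mg a day on average, a halving). When the inhibitor stops, the patient receives 10 mg, exactly as a patient without toxicity would. The halving leaves no trace.

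**Step 3: exposure only, inducer.** An event at 20 mg is followed by a cut to 10 mg on the inducer, then 10 mg alone. An on-inducer dose is equivalent to dose/f without the inducer.
- Against exposure at the event: 10/(20/f) = 10f/20.
- Against exposure at the reduced dose: 10/(10/f) = f.

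| f | Against the event | Against the reduced dose |
|---|---|---|
| 1.5 | 75% | 1.5 times |
| 2 | 100% | 2 times |
| 3 | 150% | 3 times |

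**Step 4: the undefined level.** From 20 mg, the next level down could be read as 15, 10 or 5 mg. The rise on return to 10 mg alone is 10f/d for reduced dose d. At f = 2 this is 1.33, 2 and 4 times respectively. For d = 15 it is 10 × 1.5/15 = 1.0 at f = 1.5, so in that one case nothing is undone.

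**Step 5: with the exception clause.** The patient in Step 1 stays at 5 mg. The patient in Step 3 resumes at 5 mg alone. Against the event this is 5f/20 = 38%, 50% and 75% for f = 1.5, 2 and 3. Against the reduced on-inducer dose it is 5f/10 = 0.75, 1.0 and 1.5 times. At 3-fold induction exposure therefore still rises somewhat, but stays below that at the event.

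**The case against.** The strongest reply is that the investigator already has room to act. The return sentences say what should happen, not what must. Section 3.2.3 permits dose adjustment for intolerance, section 3.4.3.1 allows study-drug changes in response to any adverse event, and section 3.4.5.2 requires a documented monthly discussion of toxicities and dose adjustments. All of this stands and softens the problem. It does not remove a written instruction that points the other way.

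Three stronger readings are tempting and not supported.
- A reader might infer that the two sets of dose rules contradict each other whenever this sequence occurs. They do not. In the 20 to 10 mg path both give 10 mg; exposure rises because induction ends. A direct conflict in tablet dose needs a reduced dose below the earlier one.
- A reader might infer that after an event at 15 mg the return takes exposure above that at the event. That assumes full induction and steady state at 15 mg. Section 3.3.3 starts 15 mg at day 7 and puts induction at 7 to 10 days, and section 1.1.3.1 allows up to two weeks to steady state, so no ratio can be relied on.
- A reader might take the cut from 10 to 2.5 mg as a 4-fold exposure factor for moderate inhibitors. The similar-AUC aim is stated only for inducers.

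Frequency is also unknown. Strong inducers are discouraged, and new drugs need prior consultation. Three of the six inducers named are anti-epileptics, which section 3.2.2.5 accepts as supportive care. But a patient already on one at entry has no earlier RAD001 dose to return to.

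**Conclusion.** The concern holds as a minor dosing-safety gap. Followed literally, both return rules can undo a toxicity reduction made during co-administration. In tablet dose this needs no assumption: the 5 mg patient goes back to 10 mg, and the patient cut to every-other-day dosing on an inhibitor goes back to the full earlier dose. In the 20 to 10 mg path it happens in exposure only, to about 100% of that at the event at 2-fold induction (75% to 150% over the assumed range), and this rests on dose-proportional AUC. The missing levels above 10 mg are a real but smaller gap.

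The sequence (interacting drug needed, toxicity reduction while on it, drug then stopped) is probably uncommon, and the documents give no rate. A reader might infer that the trial's statistical conclusions are at risk; nothing supports that. Sample size, alpha, power and the 6-month progression-free survival analysis are unaffected.

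**What to change.** 1. Add to both return-dose sentences in section 3.3.3: *unless the dose was reduced for toxicity during co-administration; in that case resume at least one Table 3.0 level below the dose used before the inducer or inhibitor was started, and do not re-escalate.* State also what applies if that earlier dose was already 5 mg every other day, since Table 3.0 has nothing lower.
2. Add a note to Table 3.0: after toxicity on an inducer, no restart may exceed the dose at the event, and a reduction to the next level must be below the dose at the event (for example 20 to 10 mg, 15 to 10 mg, 10 to 5 mg).

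A fixed on-inducer column with 20 mg as level 0 and 10 mg as level -1 may look neater but should not be used. A restart at the initial dose after an event at 15 mg would become 20 mg, and an event at 10 mg in the first week would be met with no reduction.

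The cost is one clause in two sentences and one table note, with no change to eligibility, visits, sample size or analysis. The downside is that a few patients may resume at a lower dose than they could tolerate.
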